# 8.5. Safety Oversight

This study will have an independent DSMB to oversee subject safety and well-being as detailed in [Section 13.5]. In addition, the Study SMC consisting of the Sponsor and contract research organization personnel will regularly monitor all aspects of subject safety throughout this study, including but not limited to all SAEs, AEs, clinical laboratory data, ECG data, MRI, weight loss, and other relevant safety data such as physical examination findings. The Study SMC will meet at regular intervals, but no less than monthly to review the emerging safety data. The details of the

Confidential Page 87 of 115

safety reviews and composition of the SMC will be detailed in the Safety Management Plan and the SMC charter, respectively.

### 9. CLINICAL MONITORING AND COMPLIANCE

### 9.1. Study Monitoring

Monitoring procedures approved by the Sponsor will be followed in order to comply with GCP guidelines. Remote and on-site checking of the eCRFs for completeness and clarity, cross-checking with source documents, and clarification of administrative matters will be performed.

The study will be monitored by the Sponsor or its designee. Monitoring will be done by personal visits, whenever possible, from a representative of the Sponsor who will review the eCRFs and source documents. This CRA will be qualified by training, education and experience to monitor the progress of sites participating in a clinical study and to ensure that it is conducted, recorded, and reported in accordance with the protocol, standard operating procedures (SOPs), GCP and the applicable regulatory requirements.

The interval between monitoring visits will depend on the recruitment rate and the complexity of the study. Source data verification (SDV) is an essential part of the monitoring process and the Investigator must grant direct access to the original subject's source documents. The extent and nature of monitoring will be described in detail in the monitoring plan.

In the event of pandemics, alternative monitoring measures may be required if on-site monitoring is not permitted and deviations to the study monitoring schedule are necessary. If it is not possible to follow the recommended monitoring schedule of onsite visits due to national, local, or site-specific restrictions, possible temporary, alternative measures may be implemented to maintain proper oversight of the clinical trials. All monitoring deviations related to the pandemic should be well-documented to enable appropriate evaluation of the clinical trials.

Remote SDV will be allowed if the site and Principal Investigator agree to this method of monitoring due to pandemic restrictions for onsite monitoring visits. To facilitate remote SDV, scans of source document worksheets, assessment forms, and other required documentation will be sent to the monitor. Monitors should be trained on remote SDV procedures. No protected health information should be scanned and sent to the monitors. If a site allows the monitors to have access to their electronic medical records, this should only be available to the monitor during the time of the remote visit. Site staff should be available to respond to monitors questions during the remote monitoring visit.

# 9.2. Data Quality Assurance

The Sponsor's representatives and regulatory authority inspectors are responsible for contacting and visiting the Investigator for the purpose of inspecting the facilities and, upon request, inspecting the various records of the study (e.g., eCRFs and other pertinent data), provided that subject confidentiality is respected.

The Study Monitor is responsible for inspecting the eCRFs at regular intervals throughout the study to verify the following: adherence to the protocol; completeness, accuracy, and consistency of the data; and adherence to local regulations on the conduct of clinical research. The CRA should

Confidential Page 88 of 115

have access to study subject medical records and other study-related records needed to verify the entries on the eCRFs. The Investigator must agree to cooperate with the CRA to ensure that any problems detected in the course of these monitoring visits are resolved.

In accordance with ICH GCP and the Sponsor's audit plans, this study may be selected for an audit. Inspection of site facilities (e.g., pharmacy, drug storage areas, laboratories) and review of study-related records may occur in order to evaluate the study conduct and compliance with the protocol, ICH GCP, and applicable regulatory requirements.

# 9.3. Audits and Inspections

Regulatory authorities, the IRB/IEC, and/or the Sponsor's clinical quality assurance group, or its designee, may request access to all source documents, eCRFs, and other study documentation for on-site audit or inspection. Direct access to these documents must be guaranteed by the Investigator, who must provide support at all times for these activities.

# 9.4. Archiving Study Documents

Investigators are required to maintain all study documentation, including documents created or modified in electronic format, for at least 15 years following the completion of the study. ICFs and adequate records for the receipt and disposition of all study drug must be retained for a period of 2 years following the date a marketing application is approved for the drug for the indication for which it is being investigated, or, if no application is to be filed or if the application is not approved for such indication, until 2 years after the investigation is discontinued and the FDA and other applicable Regulatory Authorities are notified, unless a longer period is required by applicable law or regulation. The Investigator must not discard any records unless given written authorization by the Sponsor.

Investigators are responsible for all study records and the accuracy of the subject data and source documents. It is required that Investigators contact the Sponsor or its designee for the following:

- If the study files are relocated to another facility or the custodian of the records is changed at any time while the records are being stored.
- If the Investigator delegates responsibility for these documents to another person.

Subject identity information will be maintained for 15 years unless applicable law or regulation requires a longer period.

#### 10. STATISTICAL METHODS AND DATA ANALYSIS

#### 10.1. General Considerations

All statistical processing will be performed using the most current version of SAS® at the time of the analysis. Data summaries and listings will be provided for all baseline variables collected (subject disposition, all demographic and baseline characteristics, prior and concomitant medications, and study drug compliance), all efficacy outcomes, all safety outcomes (deaths, AEs, clinical laboratory values, vital signs, ECG assessments, physical examination, and neurological examination), all fluid and imaging biomarker outcomes, and CSF and plasma concentrations of

Confidential Page 89 of 115

ALZ-801, tramiprosate, and 3-SPA. Individual data will be listed and sorted by treatment, subject ID, visit, and time point.

Summary statistics for continuous measurements will be reported using the number of study subjects with data values, mean, median, standard deviation (SD), minimum, and maximum. For continuous efficacy outcomes 95% confidence intervals will be provided.

Summary statistics for categorical variables will be reported using the number and percentage of study subjects within each level of the variable.

Baseline values for a given variable are defined as the last values collected prior to the first administration of ALZ-801.

A detailed SAP will be developed and finalized prior to the final database lock, and submitted to regulatory authorities per local guidelines. Any analyses after database lock that represent deviations from the final approved SAP will be described and justified in the clinical study report.

### 10.2. Endpoints for Statistical Considerations

See Section 4.2 for endpoints for statistical considerations.

### **10.3.** Determination of Sample Size

#### 10.3.1. Primary Clinical Outcome

The total study sample size will be approximately 300 subjects or 150 subjects per treatment group (TRT). The sample size was determined based on efficacy data from an AD study with tramiprosate, the active agent in ALZ-801. These efficacy data were observed with tramiprosate 150mg BID, which provides plasma exposures similar to ALZ-801 at 265mg BID, the dose used in this study. In the previous 78-week AD study, the APOE4/4 subpopulation treated with tramiprosate showed approximately 5.0 point difference from placebo (benefit) on ADAS-Cog 11 in Mild AD subjects with baseline MMSE scores of 22-26 [Abushakra et al. 2017].

For the primary efficacy outcome of ADAS-Cog 13, this study is powered to detect a 3.0 point difference between ALZ-801 and placebo in the CBL to Week 78. This assumes a within-treatment SD of approximately 8.1 in the drug arm and 5.6 in the placebo arm.

A sample size of 125 subjects per arm will provide approximately 90% power to show a 3-point difference between the two treatment groups at a significance level of  $\alpha = 0.05$  (2-sided). The drop-out rate is estimated to be approximately 17% at 78 weeks, thus a total of 300 subjects enrolled would provide approximately 250 completers or approximately 125 per arm.

#### 10.3.2. Fluid Biomarker Outcome

**CSF Sub-study**: For CSF p-tau181, the primary fluid biomarker outcome, sample size determination was based on data from two Early AD studies with anti-amyloid antibodies that showed significant (13% to 17%) reduction in CSF p-tau over 78 weeks [Tolar et al. 2020b]. We therefore assumed the following:

• Expected baseline mean CSF p-tau181 level in each study arm : 90 to 110 pg/mL

Confidential Page 90 of 115

- CSF p-tau181 levels at week 78 are expected to be approximately 15% lower than baseline in the ALZ-801 arm and to remain stable in the placebo arm, with approximately 15% difference in CBL between ALZ-801 and placebo
- Expected difference:  $\Delta = 15 \text{ pg/mL}$
- Confidence level:  $1-\alpha = 95\%$
- 2-sided test on paired samples

A sample size of 45 subjects per arm provides > 90% power to detect a delta of 15 pg/mL (decrease) in CSF p-tau181 at 78 weeks, assuming a SD of 25 pg/mL; and provides power of approximately 90% assuming a SD of 30 pg/mL. A total of 60 subjects enrolled would provide approximately 48 completers per arm, assuming 20 % drop out rate in the CSF sub-study.

For plasma p-tau181, it is assumed that the difference in CBL between ALZ-801 and placebo CBL will be similar to CSF, namely a 15% difference. A sample size of 125 completers per arm is therefore expected to provide > 90% power.

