### 10.8. Biomarker Analyses

#### 10.8.1. Cerebrospinal Fluid Biomarker Analyses

Serial CSF samples from the baseline, Week 52 and Week 78 visits will be stored and batched for analyses. Samples from multiple subjects and study sites will be analyzed in batches, at a single central laboratory, using standardized procedures and validated assays, or well performing, widely accepted CSF assays if not validated.

Confidential Page 95 of 115

The CSF biomarker analyses will be performed on subjects (CSF sub-study) who have a baseline and at least one post-baseline CSF biomarker sample. The change from baseline and percent change from baseline in CSF biomarkers will be summarized by visit and treatment group. The between groups comparisons of change from baseline in each CSF biomarker will be analyzed using an MMRM model with treatment, the use of concomitant AD medications (AChEI or none), age group (50 through 65 years or > 65 years from the result of the Screening – Part 1 Visit), gender, disease severity based on MMSE at the Baseline Visit, baseline CSF biomarker level, visit, and treatment by visit interaction in the model.

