4.3 Exploratory Fluid Biomarker Outcomes

Exploratory Plasma Biomarker Outcomes

Plasma biomarkers are performed in all subjects. For plasma p-tau₁₈₁, a difference (reduction) of ~15% in CBL may be expected between ALZ-801 and placebo, similar to the effects seen in the lecanemab clinical trials (Leqembi FDA label 2023). No formal statistical powering was conducted for this outcome.

Exploratory CSF Biomarker Outcomes

The CSF sub-study target enrollment is a total of 120 subjects who are to provide serial CSF samples at 52 and 78 weeks, with approximately 96 subjects expected to provide CSF at Week 78 study endpoint. Early AD studies with the approved anti-amyloid antibodies (aducanumab and lecanemab) showed significant (13% to 22%) reduction in CSF p-tau₁₈₁ over 78 weeks. This CSF sub-study sample size is similar to that of the aducanumab Phase 3 studies (Budd-Haeberlein 2022). No formal statistical powering was conducted for this outcome.

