In the Protocol version 3.0, CSF and plasma p-tau₁₈₁ were designated as primary fluid biomarker outcomes. In this SAP, these imaging and fluid biomarker outcomes are being designated as exploratory outcomes. In 2018, the National Institute on Aging-Alzheimer's Association (NIA-AA) proposed that research criteria for AD trials be based on positive amyloid and tau on either CSF biomarkers or PET scans (Jack 2018). In the ongoing 2023 update to these criteria, there is increased focus on the use of plasma biomarkers as research criteria for clinical trials. However, assay validation for these plasma biomarkers and development of standard cut-off values is still evolving. To date, the correlation of drug effects on the core plasma and CSF AD biomarkers to clinical benefit remains unclear. For these reasons, plasma and CSF biomarkers are designated as exploratory biomarkers.

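### The CSF p-tau181 power in Protocol 10.3.2 is that of a one-arm paired test; for the planned between-arm comparison it is about 80% (SD 25) and 65% (SD 30) with 45 per arm

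*Protocol*

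**What the plan says.** Protocol 10.3.2 calls CSF p-tau181 the primary fluid biomarker outcome. It assumes a baseline mean of 90 to 110 pg/mL in each arm, a fall of about 15% on ALZ-801, and placebo levels "to remain stable in the placebo arm, with approximately 15% difference in CBL between ALZ-801 and placebo". The difference to be detected is 15 pg/mL at 95% confidence, and the test is given as "2-sided test on paired samples".

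The power statement is "A sample size of 45 subjects per arm provides > 90% power to detect a delta of 15 pg/mL (decrease") at an SD of 25 pg/mL; the same sample size "provides power of approximately 90% assuming a SD of 30 pg/mL". On attrition: "A total of 60 subjects enrolled would provide approximately 48 completers per arm", with 20% dropout.

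The planned analysis is in Protocol 10.8.1: "The between groups comparisons of change from baseline in each CSF biomarker will be analyzed using an MMRM model", with baseline CSF level among the covariates.

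The SAP changes the status of the outcome. Section 5 says: "In this SAP, these imaging and fluid biomarker outcomes are being designated as exploratory outcomes". Section 4.3 says of the CSF outcome: "No formal statistical powering was conducted for this outcome".

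**The concern.** The two arms are independent randomised groups, so the only pairing available is baseline with Week 78 within a subject. A paired test of that kind asks whether the drug arm has moved from its own baseline. It leaves the sampling variation of the placebo arm out of the calculation. The effect in 10.3.2 and the analysis in 10.8.1 both concern the difference between arms, whose variance for the same SD and n per arm is twice that of a single arm's mean change.

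If the quoted power belongs to the one-arm test, the sub-study is less able to detect a 15 pg/mL difference than the protocol says. At SD 30 the chance of missing a true difference of that size would be about 32% to 35% (48 or 45 per arm), not about 10%. A null CSF result read against 10.3.2 would then look stronger than it is.

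**Working it through.** **Inputs (Protocol 10.3.2).** Difference d = 15 pg/mL; SD s = 25 or 30 pg/mL; two-sided alpha 0.05; 45 per arm for the power statement; 60 × (1 − 0.20) = 48 completers per arm. The text does not say whether s is the SD of change or of the level. It is taken here as the SD of change, the natural meaning in a paired test.

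**1. The stated figures as a one-arm paired t-test.** Noncentrality = (d/s) × √n, df = n − 1 = 44, critical t = 2.015.

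- SD 25: (15/25) × √45 = 4.02; power 97.6% (stated: above 90%).
- SD 30: (15/30) × √45 = 3.35; power 90.7% (stated: about 90%).

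Both figures reproduce.

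**2. The between-arm comparison, unadjusted two-sample t-test.** Noncentrality = (d/s) × √(n/2), df = 2n − 2.

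| n per arm | SD | Noncentrality | Power |
|---|---|---|---|
| 45 | 25 | 0.6 × √22.5 = 2.85 | 80.4% |
| 45 | 30 | 0.5 × √22.5 = 2.37 | 65.0% |
| 48 | 25 | 0.6 × √24 = 2.94 | 82.9% |
| 48 | 30 | 0.5 × √24 = 2.45 | 67.9% |

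A one-sided alpha of 0.05 with 48 per arm does not match either: the normal approximation gives 90.2% and 79.0%.

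**3. What 90% would need.** With 48 per arm, the SD of change must be about 22.4 or less, or the true difference must be 16.7 pg/mL (SD 25) or 20.1 pg/mL (SD 30). At a difference of 15, the completers needed per arm are 60 (SD 25) or 86 (SD 30). With 20% dropout that is 60/0.8 = 75 or 86/0.8 = 107.5, rounded up to 108, enrolled per arm.

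**4. Range under baseline adjustment.** The documents give no correlation, so r is an assumption. Residual SD = s × √(1 − r²), where r is the correlation, in absolute value, between baseline and change.

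| Assumed r | n per arm | Power, SD 25 | Power, SD 30 |
|---|---|---|---|
| 0.3 | 48 | 86.2% | 72.0% |
| 0.5 | 48 | 91.9% | 79.9% |
| 0.5 | 45 | 90.2% | 77.3% |

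Power reaches 90% at r of about 0.44 (SD 25) and 0.66 (SD 30) with 48 per arm, or 0.50 and 0.69 with 45.

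**5. If 25 and 30 were SDs of the level.** The same residual formula applies, with r now the correlation between baseline and Week 78. With 45 per arm and an assumed r of 0.7, power is 97.6% and 90.7%.

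**6. The neighbouring calculations.** By the normal approximation, Protocol 10.3.1 (3 points, SDs 8.1 and 5.6, 125 per arm) has standard error √((8.1² + 5.6²)/125) = 0.881, a ratio of 3.41 and power of about 93%. Protocol 10.3.3 (68 mm³, SDs 165 and 147, 125 per arm) has standard error 19.8, a ratio of 3.44 and power of about 93%. Both are consistent with their stated power as two-sample comparisons, so the paired test is peculiar to the CSF outcome.

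**The case against.** The strongest reply is that the 80% and 65% depend on what the SD means. Section 10.3.2 frames its assumptions in levels, so 25 and 30 could be SDs of the level. A baseline-adjusted between-arm comparison with a baseline-to-Week 78 correlation of 0.7 would then give the stated power (step 5). The planned MMRM does adjust for baseline, and it includes anyone with at least one post-baseline sample, so an unadjusted completer t-test probably understates its power. The numbers are also correct for the test the protocol names. The fault is a test that does not match the comparison, rather than a slip in arithmetic. Finally, the SAP has made the outcome exploratory and disclaims formal power, and enrolment is complete.

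Much of this stands as qualification. The two-sample figures are conditional, and the impact is small. It does not rescue the text: the protocol states neither an SD of the level nor a correlation, and a paired-samples test does not describe a baseline-adjusted comparison of two arms. The SAP's reclassification removes the consequence for inference but leaves the power figure in the protocol uncorrected.

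**Conclusion.** The concern holds. The stated power is that of a one-arm paired test and not of the planned between-arm comparison. With 25 and 30 pg/mL as SDs of change and no gain from baseline adjustment, power for a 15 pg/mL difference is about 80% and 65% with 45 per arm, or 83% and 68% with 48. Assumed baseline-change correlations of 0.3 to 0.5 raise the 48-per-arm figures to 86–92% (SD 25) and 72–80% (SD 30).

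The consequence is limited. CSF p-tau181 lies outside the hierarchical sequence of Protocol 10.7.1 and the graphical procedure of SAP 8.1.5, so no confirmatory claim depends on it. The protocol still presents it as a primary fluid biomarker outcome with about 90% power or more, so the figure should be corrected.

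**What to change.** In Protocol 10.3.2, remove the reference to a paired-samples test. Say instead that the power is for a two-sided two-sample comparison of change from baseline, with 25 or 30 pg/mL taken as the SD of change and any gain from baseline adjustment ignored: about 83% (SD 25) and 68% (SD 30) with 48 completers per arm, or 80% and 65% with 45. If the sponsor meant the SD of the level, or relies on baseline adjustment, it should say so, give the correlation assumed, and quote the power that follows.

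This is a wording change in one protocol section. The SAP, the analysis and enrolment are unaffected. The cost is a less favourable power statement.

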#### 10.3.3. Imaging Biomarker Outcome

For total hippocampal volume, the power calculation is based on the assumption that the placebo arm experiences hippocampal atrophy of 6% while the drug arm experiences approximately 4% atrophy over 78 weeks. The baseline hippocampal volume is assumed to be approximately 3100 mm^3, the delta is expected to be 68 mm^3, with SD of 165 mm^3 and 147 mm^3 for the drug arm and placebo arms, respectively. A sample size of 125 per arm provides > 90% power to detect a 40% attenuation in hippocampal atrophy compared to placebo at 78 weeks, at a significance level of  $\alpha = 0.05$  (2-sided).

# 10.4. Subject Stratification

Randomization will be stratified by use of concomitant AD medications (AChEI or none), age (50 through 65 years or > 65 years at the Screening – Part 1 Visit), gender, and disease stage (MMSE  $\leq$  26 or > 26 at the Baseline Visit). It is expected that approximately 60% will be AD subjects with MMSE 22-26 (inclusive), and approximately 40% will be AD subjects with MMSE 27–30 (inclusive).

# 10.5. Study Populations

The criteria for study populations are described below and in the SAP. A subject classification document will be prepared and signed before database lock.

#### **10.5.1.** Safety Population

The Safety population will include all study subjects who received at least one dose of study drug. All safety analyses will be conducted on this population.

#### 10.5.2. Modified Intent-to-Treat Population (mITT)

The mITT population will include all study subjects who have received at least one dose of study drug, have one baseline assessment, and have also completed at least one scheduled post-baseline

Confidential Page 91 of 115

visit with at least one valid post baseline efficacy assessment. All primary and secondary efficacy analyses will be conducted on this population.

#### 10.5.3. Per Protocol Population (PPP)

The PPP will include all study subjects who have completed the study and who are at least 80% compliant with study drug for the duration of their study participation. The PPP will be used for sensitivity analyses of the primary and secondary efficacy endpoints.

#### 10.5.4. Completer Population (CP)

The CP will include all randomized subjects who receive at least one dose of study drug, being on treatment until Week 78 and have completed the study, regardless of compliance with study drug. Subjects who discontinue treatment prematurely will not be included in this population even if they adhere to the scheduled visits. The CP will be used for sensitivity analyses of the primary and secondary efficacy endpoints.

#### 10.5.5. Pharmacokinetic Population

The PK population will include all treatment assigned study subjects who have received at least one dose of active treatment and have at least one evaluable post-dose PK sample.

